#### 17. Efficacy Evaluations

#### 17.1. Data Sets Analysed

The principle of intention-to-treat, as far as practically possible, will be the main strategy of the analysis adopted for the primary outcome and all secondary outcomes. These analyses will be conducted on all randomised participants, in the group to which they were randomised, and for whom the outcome(s) of interest have been observed/measured. No imputations will be made.

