#### 17.4.5.1. Derivation

The post-extubation oxygen supplementation details can be found on the Post Mechanical Ventilation follow up CRF. The start point for the duration of post-extubation oxygen supplementation will the date and time of final successful extubation as described in section 17.4.1.1, if this has been observed.

The end point will be the final date and time (MACRO variable PMV02DTD) that any type of oxygen supplementation (NIV, high-flow  $O_2^2$  or low-flow  $O_2^3$ ) is ended as indicated by the final observation for which the MACRO variable PMVS02SC (Supplementary O2 stopped?) = "Yes".

If oxygen supplementation is stopped and then restarted this time will be included in the overall time of post-extubation respiratory support. If no oxygen supplementation is recorded then time on postextubation respiratory support will be assumed to be zero.

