#### 17.4.5.2. Analysis

Descriptive statistics will be presented split by treatment and overall for the time from successful extubation to cessation of post-extubation oxygen supplementation. The summaries will be presented as median and interquartile range as the data is likely to be skewed.

The comparative analysis will be as described in 17.4.1.2 but will just involve the two-sample t-test, a linear mixed effects model will not be used for this outcome.

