## 17.4.7.1. Derivation

The post-extubation NIV respiratory support details can be found on the Post Mechanical Ventilation follow up CRF. The start point for the duration of post-extubation respiratory support will the date and time of final successful extubation as described in section 17.4.1.1, if this has been observed.

The end point will be the final date and time (MACRO variable PMV02DTD) that NIV is ended as indicated by the final observation for which the MACRO variable PMVTOSPC (Type of Supplementary O2) = "NIV".

If NIV is stopped and then restarted this time will be included in the overall time of post-extubation respiratory support. If no NIV is recorded then time on post-extubation respiratory support will be assumed to be zero.

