## 18. Missing data and withdrawals

Missing data will be quantified for all outcomes presented in the final analysis report. Where known, reasons for missingness will be given.

Withdrawals from trial will be summarised and presented as line listings detailing:

- 1. Site
- 2. Time from randomisation to withdrawal
- 3. Decision to withdraw participant made by:
  - a. Clinician
  - b. Parent/person with parental responsibility
  - c. Both clinician and parent/person with parental responsibility
- 4. Reason for withdrawal:
  - a. Death
  - b. Lost to follow-up
  - c. Transfer to non-participating site
  - d. Withdrawal of consent for follow-up
  - e. Other (specify)

Every effort will be made to collect follow-up data even in the event of participants discontinuing the trial intervention. In the case of withdrawals from study, available data will still be included using an intent-to-treat approach.

#### 19. Additional analyses Additional analysis 1

A sensitivity analysis of the primary analysis will be done to assess the robustness of the primary analysis. This will be done using a Cox proportional hazards model and will allow the censoring of patients who do not observe the primary endpoint of successful extubation. The start-point and end point for patients having the event of successful extubation will be the same as those defined in section 17.4.1.1. For patients who do not have a successful extubation recorded these will be censored at the last date and time (OAODATXD) an observation is recorded on the Observations and Outcomes CRF. The cox proportional hazards model will include the allocated treatment and time on ventilation prior to randomisation as covariates.

#### Additional analysis 2

A subgroup analysis of the primary outcome will be undertaken, This was based on a recommendation from the Trial Steering Committee who met on the 20th February 2024.

The subgroup analysis will examine the primary outcome stratified by whether the baby was born prematurely or not and will include an interaction term between treatment and prematurity in the linear mixed effect model described in 18.4.1.2.

Results will be presented from the model with the interaction result alongside.

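### Post-extubation oxygen and NIV durations are set to zero when nothing is recorded, with no requirement for a completed form, so an absent form can count as 0 hours instead of missing

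*SAP*

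**What the plan says.** Two secondary durations come from one form. For oxygen (SAP 17.4.5.1): "The post-extubation oxygen supplementation details can be found on the Post Mechanical Ventilation follow up CRF". SAP 17.4.7.1 names the same CRF for NIV.

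Each derivation ends with a zero rule. For oxygen: "If no oxygen supplementation is recorded then time on postextubation respiratory support will be assumed to be zero". For NIV: "If no NIV is recorded then time on post-extubation respiratory support will be assumed to be zero". Neither mentions an absent, blank or incomplete form.

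The clock starts at "final successful extubation as described in section 17.4.1.1, if this has been observed".

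The general rules are elsewhere. SAP 17.1 restricts analyses to randomised infants "for whom the outcome(s) of interest have been observed/measured. No imputations will be made". SAP section 18 adds: "Missing data will be quantified for all outcomes presented in the final analysis report".

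Both durations are summarised by median and interquartile range. On testing, SAP 17.4.5.2 says "The comparative analysis will be as described in 17.4.1.2 but will just involve the two-sample t-test", and SAP 17.4.7.2 does the same. The t-test in 17.4.1.2 is on natural-log data. No offset or other treatment of zeros is given.

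**The concern.** The zero rule does not separate two kinds of infant. One has a completed post-ventilation form showing no support, so zero is a true value. The other was extubated but has no later form, so the duration is unknown. A programmer following the derivation literally would code both as 0 hours. For the second infant that is single imputation at the shortest possible duration, and the infant no longer appears as missing.

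Such infants are foreseeable. Under Protocol 8.7.2.2, complete withdrawal stops further data apart from serious adverse events. Protocol 8.8 gives transfer to another hospital as an example of loss to follow-up. SAP section 18 lists loss to follow-up, transfer to a non-participating site and withdrawal of consent among the withdrawal reasons.

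The SAP is more careful elsewhere: the LRSQ analysis uses only fully completed questionnaires (17.4.9.2), and the primary analysis is complete-case with a sensitivity analysis (17.4.1.2). The independent programming in SAP section 21 covers the primary and safety analyses, so it would not catch a coding choice here.

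At stake are an accurate missing-data count and honest summaries for two secondary outcomes. The treatment comparison is also at stake if zeros are later made usable.

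**Working it through.** **1. The rules applied to four kinds of infant**

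| Infant | 17.4.5.1 / 17.4.7.1, read literally | 17.1 and section 18 |
|---|---|---|
| No successful extubation observed | No start point | Missing |
| Extubated, form shows support | Observed duration | Observed duration |
| Extubated, completed form shows none | 0 h | 0 h, observed |
| Extubated, no later form | 0 h | Missing, counted |

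Only the last row conflicts. The start-point condition removes the first row but not the last. The SAP does not say which rule prevails.

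**2. Where a false zero can act**

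- Median, interquartile range and missing-data count: directly.
- Planned t-test: ln(0) is undefined, so a zero, true or false, cannot enter. It must drop out or be given an offset that the SAP does not state.

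**3. Design figure used below**

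The plan has no figure for missing forms, so only the arm size is borrowed. The formula in Protocol 11.3 is n = (z₁₋α/₂ + z₁₋β)² [ln(1+κ₁²) + ln(1+κ₂²)] / {ln δ − ½[ln(1+κ₂²) − ln(1+κ₁²)]}². With κ₁ = 2.5/4.83, κ₂ = 2.5/4.08 and δ = 4.08/4.83, it gives 99.5 → 100 per group (80% power) and 133.2 → 134 (90% power). Then 134/0.95 = 141.05 → 142 per group, 284 in total. All reproduce.

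**4. Illustration only: what false zeros would do if an offset or rank test were adopted**

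If 2–5% of infants lacked a form (assumed), 284 × 0.02 to 284 × 0.05 is about 6 to 14 infants.

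*Log with offset c.* Assume 142 per arm, identical true durations, log-SD 0.8, and forms missing in 2% of arm A and 5% of arm B. With m the mean of ln(x + c), the shift is −(0.05 − 0.02)(m − ln c). For a 48 h median and c = 1, m is about 3.9, so the shift is −0.117 and the ratio is exp(−0.117) = 0.89. The arm SDs become 0.94 and 1.14, so SE = √[(0.94² + 1.14²)/142] = 0.124. The null is then rejected in about 15.6% of trials.

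| Assumed median | c = 1: ratio, rejection | c = 0.5: ratio, rejection |
|---|---|---|
| 24 h | 0.91, 13.8% | 0.89, 15.6% |
| 48 h | 0.89, 15.6% | 0.87, 17.4% |
| 96 h | 0.87, 17.4% | 0.85, 18.9% |

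Swapping the arms reverses the direction. With 5% missing in both arms the ratio is 1.00, but the log-SD rises from 0.76–0.79 to 1.02–1.38.

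*Rank test.* Five extra false zeros among 142 in one arm move the Mann–Whitney probability from 0.500 to 137 × 0.5/142 = 0.482. Its standard error is √[285/(12 × 142 × 142)] = 0.034, so the shift is about half a standard error.

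*Median.* Five extra zeros move it about 2.5 ranks in 142.

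**The case against.** The strongest reply is that the passages can be read together without conflict. The zero rule never mentions a missing form. Its ordinary meaning may be that an infant who was followed up and has no support recorded had none, while 17.1 excludes anyone whose outcome was not observed. Data handling also limits the problem. Protocol 8.2 has daily data collection to hospital discharge. Protocol 8.4.2 requires post-extubation oxygen and saturation readings from standard care to be transcribed. Protocol 14.2 requires missing data to be explained, and 14.3.2 has missing values queried. A wholly absent form should usually be a known gap.

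This narrows the point but does not remove it. The derivation is the text a programmer follows, and it makes zero depend on nothing being recorded. Querying can explain a gap but cannot recover data after withdrawal. The two readings put different infants in the analysis.

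A reader might go further and infer that infants with missing forms receive the best possible result in the treatment comparison, so that any imbalance in missing forms becomes a false treatment effect. The documents do not support that. The log-scale t-test cannot use a zero, and 17.1 can be read to exclude absent forms. Nor do they support a specific bias such as a 13% reduction. That figure, from 5 × ln(49)/142 = 0.137 and 1 − exp(−0.137) = 12.8%, needs an assumed 48 h duration, an assumed +1 offset and five excess missing forms in one arm.

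**Conclusion.** The point holds as a conflict between two rules in the SAP. Under the literal derivation, an extubated infant with no later form is scored 0 hours and is not counted as missing. Under 17.1 and section 18 the same infant is missing.

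As written, the effect is confined to the medians, interquartile ranges and missing-data counts of two secondary outcomes, and on a median it is likely to be small. It would reach the comparison only through an offset or rank test. In the illustrations an offset makes it material and a rank test makes it minor. Both rest on assumed inputs, because the documents give neither a missing-form rate nor typical oxygen or NIV durations. The direction is unknown, and equal missingness creates no difference between arms by itself. The primary outcome, sample size and safety outcomes are unaffected. It should be corrected, but it does not threaten the main result.

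**What to change.** In SAP 17.4.5.1 and 17.4.7.1, replace the last sentence with a rule of this kind: the duration is zero only when a Post Mechanical Ventilation follow up CRF was completed after final successful extubation and shows no oxygen (or, for 17.4.7.1, no NIV); if there is no such completed form, the duration is missing and is reported by arm under section 18.

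The cost is one sentence in each derivation and no new data. In the offset illustration, keeping absent forms as missing returns the ratio to 1.00, provided missingness is unrelated to outcome; the counts by arm help a reader judge that.

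The SAP separately needs to say how genuine zeros are handled in the log-scale t-test. Settle the rule above first, so that whatever method is chosen receives only true zeros.

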#### 17.4.5.2. Analysis

Descriptive statistics will be presented split by treatment and overall for the time from successful extubation to cessation of post-extubation oxygen supplementation. The summaries will be presented as median and interquartile range as the data is likely to be skewed.

The comparative analysis will be as described in 17.4.1.2 but will just involve the two-sample t-test, a linear mixed effects model will not be used for this outcome.

#### 17.4.6. Secondary Outcome 5: Use of steroids to assist extubation

This outcome will assess if there is a difference in the use of steroids to assist extubation between arms.

## 17.4.6.1. Derivation

The details for steroid use during extubation can be found on the Observations and Outcomes CRF indicated where the variable OAOSTERC= "Yes".

#### 17.4.6.2. Analysis

This binary outcome will be presented in a two-way frequency table (allocated treatment group by use of steroids during extubation) and a Chi-squared test will be used to test association between allocation and use of steroids if the expected cell counts a greater than five and Fisher's exact test will be used if they are not. The Chi-squared test statistic and corresponding p-value will be presented for the test.

The relative risk between arms of having to use steroids during extubation will be presented along with 95% confidence interval.

#### 17.4.7. Secondary Outcome 6: Duration of post-extubation respiratory support

This outcome will assess if there is any evidence of a difference between groups in the duration of post-extubation non-invasive respiratory support, this includes all forms of non-invasive ventilation (BiPAP +/- ASB, CPAP +/- ASB, CPAP +/- pressure support).

<sup>1 BiPAP +/- ASB, CPAP +/- ASB, CPAP +/- pressure support

<sup>2 AIRVO, Optiflow, Vapotherm

<sup>3 Nasal cannula

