3.5.3 Secondary Objective(s)

- 1. To describe the impact of intervention on infants' long-term respiratory symptoms
- To describe secondary outcomes of efficacy including physiological indices and duration of other modes of respiratory support.
- 3. To assess the safety of the intervention for infants with life-threatening bronchiolitis

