3.6.2 Secondary Outcomes/Endpoints

The secondary outcome measures for the trial (WP-A) are:

For efficacy:

- 1. duration of post-extubation non-invasive respiratory support (all forms of non-invasive ventilation: e.g. nasal CPAP and nasal high low oxygen)
- 2. duration of oxygen supplementation
- 3. number of trial interventions given (both poractant and placebo)
- 4. use of steroids to assist extubation
- 5. duration of stay on PICU and in hospital;
- 6. change over time from baseline of Ventilation Index (VI), Oxygenation Index (OI) and Oxygenation Saturation Index (OSI) while mechanically ventilated, & SpO₂/FiO₂ (SF) ratio.¹
- the score (value) of parent reported outcome measure of respiratory symptoms the "Liverpool Respiratory Symptom Questionnaire" (LRSQ) at 6m (+/-1m) and 12m (+/-1m) (20);

IRAS 220853 Page **20** of **87**

¹ VI and OI are validated physiological measurements reflecting respiratory function (gas exchange) normalised for level of respiratory support provided by MV, but require blood sampling(21). OSI is a validated physiological measurement reflecting respiratory function (gas exchange) normalised for level of respiratory support provided by MV that does not require blood sampling (41). The SF ratio is a non-invasive measure of respiratory function and can be calculated in situations where invasive blood gas monitoring and MV has ceased (22).

8. time from randomisation to meeting study criteria for readiness for Spontaneous Breathing Test

For safety:

- 1. failure to administer the intervention due to any adverse event during preparatory processes (tracheal toilet or BAL)
- 2. failure to complete administration of the intervention due to any adverse event during administration of the intervention (regardless of which arm of allocation)
- 3. incidents of 'air leak' (pneumothorax and pneumomediastinum) occurring before discharge from PICU
- 4. other adverse events and serious adverse events associated with the intervention
- 5. any need to replace the endotracheal tube
- 6. parent reported readmission to hospital (all causes) up to 90 days post randomisation
- 7. death during PICU admission
- 8. all-cause mortality at 90 days post randomisation

IRAS 220853 Page **21** of **87**

Table 1: Objectives and Outcome Measures

Objectives	Outcome Measures	Timepoint(s) of evaluation of this outcome measure (if applicable)

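### SAP Secondary Outcome 6 counts only BiPAP and CPAP, although the protocol's definition of post-extubation non-invasive support also takes in high-flow oxygen

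*SAP*

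**What the plan says.** **Protocol.** Section 3.6.2, efficacy item 1, sets the outcome as "duration of post-extubation non-invasive respiratory support (all forms of non-invasive ventilation: e.g. nasal CPAP and nasal high low oxygen". Oxygen supplementation is a separate outcome, item 2. The objective served is number 2 in section 3.5.3: "To describe secondary outcomes of efficacy including physiological indices and duration of other modes of respiratory support".

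**SAP definition.** Section 9.2 keeps the protocol's label for the outcome. Section 17.4.7 then specifies that "this includes all forms of non-invasive ventilation (BiPAP +/- ASB, CPAP +/- ASB, CPAP +/- pressure support".

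**SAP derivation.** Under 17.4.7.1 the clock starts at final successful extubation. It stops when NIV ends, as "indicated by the final observation for which the MACRO variable PMVTOSPC (Type of Supplementary O2" is NIV. Time between stopping and restarting NIV is included. The default is: "If no NIV is recorded then time on post-extubation respiratory support will be assumed to be zero".

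**Where high-flow sits.** SAP 17.4.5.1 lists NIV, high-flow and low-flow as three types, each with its own footnote. NIV is BiPAP or CPAP, high-flow is "AIRVO, Optiflow, Vapotherm", and low-flow is nasal cannula. All three are pooled in Secondary Outcome 4, duration of oxygen supplementation.

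**The concern.** The protocol and the SAP use the same name for two different quantities. The protocol's examples include a form of nasal oxygen that the SAP puts in another category and leaves out of Outcome 6. The SAP gives no reason, and its change control table records only an added subgroup analysis.

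What is at stake is the meaning of a between-arm difference. If surfactant lets more infants go straight to high-flow, or come off CPAP onto high-flow sooner, Outcome 6 falls even when total time on non-invasive support is unchanged. A change of device would then be reported as shorter support.

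**Working it through.** The plan states no figure for this outcome, so there is none to reproduce. The check compares the definitions and then applies each rule to example infants.

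**1. Is high-flow inside the protocol outcome?** The examples read "all forms of non-invasive ventilation: e.g. nasal CPAP and nasal high low oxygen". The last words are garbled. They may mean high-flow oxygen, or high- and low-flow oxygen. High-flow is included on either reading, and only the status of low-flow differs.

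**2. Could the SAP wording still admit high-flow?** No. The footnotes separate high-flow devices from NIV, and the stop rule depends on the record type being NIV.

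**3. Apply the rules.** The courses below are illustrative and start at final extubation. Durations are in hours.

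| Course | SAP Outcome 6 | Protocol, high-flow reading | Protocol, high/low-flow reading | SAP Outcome 4 |
|---|---|---|---|---|
| High-flow 48 | 0 | 48 | 48 | 48 |
| CPAP 24, then high-flow 24 | 24 | 24 + 24 = 48 | 48 | 48 |
| CPAP 24 | 24 | 24 | 24 | 24 |
| High-flow 24, then low-flow 24 | 0 | 24 | 24 + 24 = 48 | 48 |
| High-flow 24, then CPAP 24 | 48 | 48 | 48 | 48 |

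The first two rows both have 48 h of support under the protocol, a difference of 0 h. Under the SAP they differ by 24 − 0 = 24 h, purely because of the device.

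The last row shows the limit of the problem. High-flow before a later NIV record is counted, because the clock runs from extubation to the end of NIV. What is lost is high-flow after the last NIV record, and all high-flow in infants with no NIV record.

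The last two columns agree in every row. On the high/low-flow reading, Outcome 4 already comes close to the protocol's item 1 under another label.

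**4. How many infants?** The documents do not say what share have high-flow and no NIV record. If the share is 30% to 70% (an assumption), then of the 2 × 134 = 268 evaluable infants in Protocol 11.3:

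- 0.30 × 268 ≈ 80
- 0.70 × 268 ≈ 188

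This range only shows scale. The mismatch does not depend on it.

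**5. Link to the test.** SAP 17.4.7.2 refers to the t-test in 17.4.1.2, which is on natural logs. ln(0) is undefined and no rule for zeros is given, so each avoidable zero adds to a difficulty the analysis already has.

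**The case against.** **The protocol version may have moved on.** The supplied protocol ends at v2.0. SAP section 5 cites v3.0 and the change control table cites v6.0. SAP 17.4.2.1 also relies on a protocol section, 8.1.4.1, that v2.0 does not contain, so later text did change. A later version may have corrected or removed the high-flow example. This stands as a limit on the finding, and it is why the first step of the fix is to check the current version. The documents show no such change.

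**The mismatch rests on one example in one place.** Protocol Table 1 and SAP 9.2 give the label without devices, and whether high-flow counts as NIV can be argued. But 3.6.2 is the only place in the protocol that spells the outcome out, and it puts high-flow in.

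**A reader might infer that Secondary Objective 2 goes unanswered.** The documents do not support that. The objective is broad, and Outcome 4 runs from the same extubation time and includes high-flow. High-flow time is pooled with NIV and low-flow, not lost.

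**A reader might also infer that unit preference for a device biases the comparison.** Randomisation is 1:1 and stratified by site, so local habits should be largely balanced between arms. The remaining risk is a shift of device caused by treatment. That is possible, but nothing in the documents shows that it is likely.

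**Conclusion.** The concern holds as a mismatch of definition. As written, SAP Outcome 6 measures time to the end of BiPAP or CPAP. Protocol 3.6.2, in the version supplied, defines a wider outcome that includes high-flow. The named outcome is therefore not measured as defined, although Secondary Objective 2 is partly served through Outcome 4.

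For an affected infant the loss is all high-flow time after the last NIV record, or the whole duration if there is no NIV record. How many infants this touches is unknown.

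The conclusion assumes that no later protocol version removed high-flow from the outcome. The primary outcome, sample size and safety analyses are not affected. It should be settled before the analysis is run.

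**What to change.** 1. Check the definition against the current protocol version, and correct the garbled oxygen wording in 3.6.2.
2. Unless a later version removed high-flow, define Outcome 6 in SAP 17.4.7 and 17.4.7.1 as NIV or high-flow. End it at the last recorded use of either, and score zero only when neither was used. Report NIV-only duration as a supplementary descriptive row.
3. If the protocol meant high- and low-flow oxygen, state how Outcome 6 differs from Outcome 4.
4. If the narrowing is intended, state and justify it, and relabel the outcome as NIV duration.
5. Whichever definition is kept, say how zeros enter the log-scale test, because infants with no support will remain.

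The cost is SAP wording and a small change to the derivation code. The type-of-support variable on the Post Mechanical Ventilation CRF appears to hold what is needed. The SAP shows only its NIV value, so confirm that high-flow is coded there.
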